Contains trade secrets and/or confidential information exempt from disclosure from 21 CFR 20.61

	automated initialization and adaptation system, as well as the use of Closed-Loop Control.
Study Population	Male and female subjects $\geq$ 18 years of age with type 1 diabetes, who are current MDI users, who have a baseline A1c at screening between 7.5 to 11%
Number of Subjects	Up to 45 subjects may sign the consent form and be screened, with the goal that 30 subjects start use of the study device, and at least 20 subjects complete the trial.
Number of Sites	1 clinical site in the United States
Main Criteria for Inclusion	
Eligibility to enroll in the study will be assessed based on the following inclusion criteria:
 
 
1. Adult subjects <math>\geq</math> age 18 years
 
2. Clinical diagnosis of type 1 diabetes for at least one year
 
3. Using a basal/bolus regimen by injection (MDI therapy)
 
4. Total daily dose <math>\geq</math> 10 units/day
 
5. Willing to use only aspart (novolog) or lispro (humalog) U-100 insulin with the study pump.
 
6. A1c <math>\geq</math> 7.5% and <math>\leq</math> 11% at screening
 
7. Not pregnant or planning a pregnancy during the time period of the study.
 
8. Has current glucagon product to treat severe hypoglycemia (injectable or nasal) at home (will provide prescription if they do not have one)
 
9. Willingness to follow study procedures and a signed informed consent form
 

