182 **Primary objective:** To demonstrate the safety of the settings initialization and adaptation  
183 algorithm when in conjunction with Control-IQ technology, by assessing the number of severe  
184 hypoglycemic events (needing assistance) compared to expected incidence

185 **Secondary objective:** Compare time in range metrics and adverse events in the full 24 hour period,  
186 overnight and during the day, after each week of settings adaptation. The number of physician  
187 overrides/physician initiated changes in pump settings will also be tracked.

188 **5.2 STUDY DESIGN**

189 This feasibility study is a prospective, single arm study, evaluating an algorithm to recommend  
190 insulin pump settings at pump start (initialization) and then adjust settings at 3 days, at 7 days,  
191 and then weekly through 13 weeks.

192 Adults (age  $\geq$  18 years of age) with type 1 diabetes, who are using multiple daily injections, will  
193 be required to collect baseline CGM data for the first 2 weeks if not already Dexcom G6 users  
194 with at least 11 of 14 days of CGM use for the 14 days prior to enrollment. They may repeat this  
195 14 day run-in period if adequate CGM data is not collected, or study staff feel it is necessary to  
196 continue to monitor their insulin dose.

197 Up to 45 subjects may sign the consent form and be screened, with the goal that up to 30 subjects  
198 start use of the study device, and at least 20 subjects complete the trial.

199 Enrollment goals for baseline A1c at screening are:

200     • At least 5 subjects with A1c 8% - 8.9%  
201     • At least 5 subjects with A1c  $\geq$  9%

202 Subjects will then proceed to pump/Control-IQ training, where an algorithm based worksheet  
203 will be used to recommend initial basal rate, carbohydrate ratio and correction factor settings.

205 Subjects will then wear the insulin pump with Control-IQ technology active, and at 3 days after  
206 training, 7 days after training, and then every 7 days will:

207     1) Upload their pump using the USB uploader  
208     2) Have their study physician review the settings recommendations on the pump download  
209        report that will appear after each download.  
210     3) Change their settings after being called by the study physician to match the new  
211        recommendations.  
212     4) Upload their pump again so the study physician can verify the settings have been changed  

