306 Each enrolled subject may participate for ~17 weeks total, to allow for 2 to 4 weeks of CGM  
307 run-in if needed, then 13 weeks of pump/AID use with weekly settings adaptation.

308 **7.4 STUDY PROCEDURES:**

309 **Event Schedule:** The CRFs will be completed by the investigator (or an authorized member of  
310 the investigator's staff) per the event schedule described below.

311

312 **Table 1.** Schedule of Visits and Procedures

	Screening Visit	CGM Run-in Visit (may be repeated after 2 weeks)	Pump and Control-IQ Training Visit	Control-IQ Use					
		2-4 weeks		3d	7d	Weekly	13w	F/U Call	UV
Visit (V) or Contact (C)	V	V	V	C	C	C	V	C	C/V
Informed Consent	X								
Eligibility Assessment	X								
Medical history/physical exam	X								
Vital Signs	X								
HbA1c (POC or local lab for inclusion criteria confirmation)	X								
HbA1c (Central lab)			X				X		
Pregnancy test (females of child-bearing potential)	X		X						
Assessment of CGM use	X	X							
Study system training		X	X						
AE Assessment		X	X	X	X	X	X	X	X
Upload device data from home				X	X	X			X
Download device data at clinic visit	X	X	X				X		X
Open Ended Interview							X		

313

314 **Baseline Data Collection:** Adults (age  $\geq$  18 years of age) with type 1 diabetes, who are using multiple daily injections, will be required to collect baseline CGM data for the first 2 weeks if not already Dexcom G6 users with at least 11 of 14 days of CGM use for the 14 days prior to enrollment. They may repeat this 14 day run-in period if adequate CGM data is not collected.

318 **Subject Completion or Early Withdrawal:** The subject completes the study approximately 17-21 weeks after enrollment, or when they choose to withdraw from the study, if earlier than the final visit

321 **Data Collection:** Investigators will assign a de-identified number to each subject and will be required to keep any study paperwork or electronic files in a secure private area. Monitoring will be conducted to help ensure that data is secure and entered within reasonable limits, consistent with a risk-based monitoring approach.

325 **Demographics:** The following demographic data will be obtained: date of birth, gender, race,  
326 ethnicity, educational level, socioeconomic status, residence, employment status, weight, height,  
327 blood pressure, pulse, and type of health insurance.

328 **Medical History:** Medical history, including existing comorbidities deemed clinically relevant  

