329 (e.g. retinopathy, nephropathy, neuropathy, history of cardiovascular events) will be collected at  
330 baseline. In addition, details specific to type 1 diabetes, including age at diagnosis, duration of  
331 disease, and previous therapy will be collected from the study subject and documented in the  
332 subject's eCRF. A new hemoglobin A1c will also be obtained at the screening visit, at  
333 randomization and at end of study.

334 **Pregnancy:** In order to reduce the risk of pregnancy, subjects of childbearing potential must  
335 agree to use an effective method of birth control while participating in this study. Acceptable  
336 methods of birth control for use in this study are barrier methods, intrauterine devices, or oral  
337 contraceptive pills. The Investigator or study staff will discuss this with the subject.

338 **Device Training:** All subjects will complete study device training before starting use of the  
339 study device. Subjects will be trained by qualified study staff using the study approved device  
340 training checklists, and will be given a copy of the Study Participant Instruction Sheet. In  
341 addition to device training, the Study Participant Instruction Sheet reviews procedures for  
342 checking ketones, and when to contact study staff for assistance.

343 All subjects will complete CGM training. Subjects who are not already Dexcom G6 users with at  
344 least 11 of 14 days of CGM use for the 14 days prior to enrollment will complete CGM run-in.  
345 They may repeat this 14 day run-in period if adequate CGM data is not collected.

346 All subjects will complete insulin pump training. The pump training visit may be extended over  
347 more than one day if needed in the judgement of the investigator. Initial pump settings will be  
348 configured by following the study settings algorithm worksheet. At the end of the pump training  
349 visit, subjects will activate Control-IQ technology

350 Subjects will wear the insulin pump with Control-IQ technology active in the outpatient setting,  
351 and have scheduled phone follow up visits at 3 days (+/- 1 day), 7 days (+/- 2 days), then weekly  
352 (+/- 3 days). A final visit in clinic will occur at 13 weeks (+/- 7 days). A post final clinic visit  
353 phone call will occur 3 days (+/- 1 day) after changing back to MDI therapy after the study  
354 devices are returned.

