## 389 **7.7 FINAL CLINIC VISIT**

390 Subjects will return all study supplies and complete the study surveys.  
391 A final central lab HbA1c will be drawn.  
392 All study devices (glucose meter, ketone meter, insulin pump and CGM) will be downloaded.  
393 Participants will be permitted to keep the blood glucometer, blood ketone meter and any  
394 remaining CGM sensors at the end of the study, but will need to return all other devices,  
395 including insulin pump and related supplies.  
396 Subjects will complete the Diabetes Impact and Device Satisfaction (DIDS) Scale, and be asked  
397 to provide their contact information for a final interview phone call.

398 Study staff will then supervise the participants transition back to their standard of care therapy.

399 • Study staff will re-evaluate the subject's baseline therapy doses, noting changes in basal  
400 rates, carbohydrate ratios, and correction factors in use at the end of the trial.

401 • Doses will be adjusted to best match the current daily insulin requirements from CSII  
402 use, typically = (total daily dose + 20%)/2, with further modification as per clinical site  
403 usual practice.

404 • Study staff will confirm subjects have carbohydrates on hand for their drive back home,  
405 and instruct subjects to check their glucose levels when they arrive at home, prior to  
406 bedtime, and at least one time overnight on the first night to monitor for hypoglycemia,  
407 reminding subjects that insulin on board can be active for the next few hours even after  
408 stopping their pump.

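### Does HbA1c need a named endpoint and a defined baseline, given that it is drawn twice by central lab and section 7.4 refers to randomization in a single-arm study?

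*Combined protocol and SAP*

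**What the plan says.** Table 1 (section 7.4) has two HbA1c rows. The first, "HbA1c (POC or local lab for inclusion criteria confirmation"), is marked at the screening visit only. The second, "HbA1c (Central lab"), is marked at the pump and Control-IQ training visit and at 13 weeks. Section 7.7 confirms the last draw: "A final central lab HbA1c will be drawn".

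The Medical History paragraph of section 7.4 gives the times in words: "A new hemoglobin A1c will also be obtained at the screening visit, at" "randomization and at end of study". Section 5.2 describes the design differently: "This feasibility study is a prospective, single arm study, evaluating an algorithm to recommend" pump settings.

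The word baseline is attached to the screening value in two places. The synopsis defines the population as those "who have a baseline A1c at screening between 7.5 to 11"%, and section 5.2 introduces its recruitment targets with "Enrollment goals for baseline A1c at screening are".

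Section 5.3 lists one primary endpoint (severe hypoglycemia) and 17 secondary endpoints (a to q). HbA1c is not among them, nor is it in the synopsis list. Section 8.1 says the statistics will include the section 5.3 outcomes and also promises descriptive statistics of glycemic outcomes at baseline and during the intervention.

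**The concern.** A laboratory measure taken before and after treatment, with no stated analysis, leaves two choices open until the data are in: whether to report the change, and from which starting value. Three names for the pre-treatment measurement appear to compete: the screening value (called baseline), a draw at a randomization that cannot occur, and the central-lab draw at training.

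The choice could matter. The screening value is selected by the 7.5 to 11% eligibility window, may come from a point-of-care or local method, and may precede training by 2 to 4 weeks of CGM run-in. Measuring change from it would favour the device, through regression to the mean and possibly through a difference between assays. The number analysed also looks uncertain: the goals are 30 starters and at least 20 completers, so up to (30 − 20)/30 = 33% of starters might have no week-13 value.

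**Working it through.** **1. Are there really three baselines?** Setting the text of section 7.4 beside Table 1:

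| Section 7.4 text | Table 1 | Method in Table 1 |
|---|---|---|
| Screening visit | Screening visit | Point-of-care or local lab, for eligibility |
| Randomization | Pump and Control-IQ training visit | Central lab |
| End of study | 13 weeks | Central lab (confirmed in 7.7) |

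Three times match three times, in the same order. The only mismatch is the name of the middle visit. Randomization there is most likely leftover wording for the training visit, the only remaining visit with an HbA1c draw.

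**2. Is the screening value defined as the reference for change?** The phrase baseline A1c at screening appears only in the description of the eligible population (synopsis) and in the enrollment goals (section 5.2). Both are recruitment uses. Inclusion criterion 6 (section 6.1.1) sets the limit on A1c at screening and does not use the word baseline. No passage defines a change in HbA1c from screening.

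**3. What would an analyst do with the schedule as it stands?** Only two values share an assay, and they bracket treatment: training visit and week 13. Table 1 gives the third value a different purpose. The matched pair follows from the schedule.

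**4. How large would the error be if someone used the screening value anyway?** The documents give no mean, SD or correlation for HbA1c, so these are assumptions: source mean μ of 7.8 to 8.6%, SD of 1.2 to 1.5, and correlation ρ of 0.80 to 0.95 between screening and central-lab values. With a normal screening value X,

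shift = (1 − ρ) × (E[X | 7.5 ≤ X ≤ 11] − μ).

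- μ = 7.8, SD = 1.5: E = 8.733. Shift = 0.20 × 0.933 = 0.187 at ρ = 0.80; 0.093 at 0.90; 0.047 at 0.95.
- μ = 8.2, SD = 1.2: E = 8.724. Shift = 0.105, 0.052, 0.026.
- μ = 8.6, SD = 1.2: E = 8.913. Shift = 0.063, 0.031, 0.016.

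The range is about 0.02 to 0.19 percentage points. Any assay difference would be extra.

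For scale, the 95% half-width of a paired mean change is t(0.975, n − 1) × SD/√n, with an assumed SD of change of 0.6 to 1.0:

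- n = 20: 2.093 × 0.6/√20 = 0.281, up to 2.093 × 1.0/√20 = 0.468.
- n = 30: 2.045 × 0.6/√30 = 0.224, up to 2.045 × 1.0/√30 = 0.373.

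The largest shift (0.187) is below the smallest half-width (0.224). These half-widths depend on sample size and are the same whether or not HbA1c is named as an endpoint.

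**5. Would a third of starters lack a final value?** That is the worst case. Section 7.5 asks those who withdraw or stop early to attend an end-of-study visit, section 7.4 places an A1c at end of study, and section 11.12 encourages those who stop the device (other than for pregnancy) to stay through the final visit. Some of these draws would fall before week 13, so the report should give the number analysed and the timing.

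**The case for a change.** The strongest case for a change is that the edit costs a few lines and needs no new draw, while silence leaves both the reporting of HbA1c and its starting value to be settled after the data are seen. The synopsis says the results will guide the product configuration, so a favourable HbA1c change may well be cited. The only value the protocol calls baseline is the one not matched to the week-13 assay. A bias smaller than the sampling error still runs in one direction.

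Part of this stands. Randomization is a wrong word and can be corrected at the next routine revision. A report of HbA1c change should name its starting value, the number analysed and the handling of early-termination draws. But the bias requires an analyst to pass over a matched central-lab pair in favour of a test marked for eligibility, and nothing in the protocol points that way. Nor does every measurement have to be an endpoint: in a descriptive feasibility study with a safety primary endpoint and weekly CGM comparisons, HbA1c can be collected as supporting description. Section 8.1 does not exclude summarising it. With one arm, naming it would not help separate the settings algorithm from the simultaneous move from injections to Control-IQ, a limit shared by every glycemic outcome here.

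**Conclusion.** The textual observations are correct: HbA1c is in no endpoint list, section 8.1 names no summary of it, and section 7.4 names a visit that a single-arm study does not have. The inference that the baseline is in conflict is not supported. One word is a clerical slip, the baseline A1c wording belongs to recruitment, and the central-lab schedule identifies the pair to compare. The rest is a gap in detail that analysts would fill sensibly.

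Followed as written, the plan gives the same results for its stated primary and secondary endpoints. The shift of 0.02 to 0.19 percentage points is hypothetical: it rests wholly on assumed means, SDs and correlations, and arises only if the screening value is used as the reference. The conclusion assumes that any reported HbA1c change is descriptive and uses the training-visit and end-of-study central-lab values. It would need revisiting if HbA1c change were promoted to a claim of effectiveness, or were computed from the screening test.

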## 381 **7.5 EARLY TERMINATION VISIT (IF APPLICABLE)**

382 Participants will be asked to come for an end of study visit in the event of withdrawal or early  
383 termination.

## 384 **7.6 UNSCHEDULED VISITS**

385 Participants may have unscheduled visits during the study period if required for additional device  
386 training or other unanticipated needs per the study investigator discretion. Study staff may adjust  
387 insulin delivery settings on the study pump at any time, and override the algorithm  
388 recommendations for safety concerns, and will document these changes.

## 389 **7.7 FINAL CLINIC VISIT**

390 Subjects will return all study supplies and complete the study surveys.  
391 A final central lab HbA1c will be drawn.  
392 All study devices (glucose meter, ketone meter, insulin pump and CGM) will be downloaded.  
393 Participants will be permitted to keep the blood glucometer, blood ketone meter and any  
394 remaining CGM sensors at the end of the study, but will need to return all other devices,  
395 including insulin pump and related supplies.  
396 Subjects will complete the Diabetes Impact and Device Satisfaction (DIDS) Scale, and be asked  
397 to provide their contact information for a final interview phone call.

398 Study staff will then supervise the participants transition back to their standard of care therapy.

399 • Study staff will re-evaluate the subject's baseline therapy doses, noting changes in basal  
400 rates, carbohydrate ratios, and correction factors in use at the end of the trial.

401 • Doses will be adjusted to best match the current daily insulin requirements from CSII  
402 use, typically = (total daily dose + 20%)/2, with further modification as per clinical site  
403 usual practice.

404 • Study staff will confirm subjects have carbohydrates on hand for their drive back home,  
405 and instruct subjects to check their glucose levels when they arrive at home, prior to  
406 bedtime, and at least one time overnight on the first night to monitor for hypoglycemia,  
407 reminding subjects that insulin on board can be active for the next few hours even after  
408 stopping their pump.

## 409 **7.8 POST STUDY PHONE CALL**

410 All participants will have a post-study phone call 3 ( $\pm 1$ ) days after the date of their final visit and  
411 transition back to their prior insulin therapy, during which the following will occur:

412 • Check on transition back to usual home diabetes care

413 • Assessment of adverse events

414

---

Confidential

Contains trade secrets and/or confidential information exempt from disclosure from 21 CFR 20.61

415 **8 STATISTICAL CONSIDERATIONS**

416 **8.1 STATISTICAL ANALYSIS:**

417 This feasibility study is a prospective, single arm study, evaluating al algorithm to recommend  
418 insulin pump settings at pump start (initialization) and then weekly for 13 weeks.

419 Descriptive statistics of the rates of severe hypoglycemia, DKA, and serious adverse events will  
420 be reported for baseline (with CGM run-in data) and compared to changes after each weekly  
421 adaptation. Additionally, descriptive statistics of glycemic outcomes will for baseline and each  
422 intervention configuration will be provided.

423 The statistics will include all primary and secondary outcomes of the study as listed in section  
424 5.3. These statistics will be calculated at the patient-level, and a sub-analysis of daytime vs.  
425 nighttime statistics will be provided.

426

427

428 **9 RISKS AND BENEFITS**

429 **9.1 POTENTIAL RISKS AND BENEFITS OF THE DEVICE**

430 Risks and Benefits are detailed below. Loss of confidentiality is a potential risk; however, data  
431 are handled to minimize this risk. Hypoglycemia, hyperglycemia and ketone formation are  
432 always a risk in participants with diabetes and participants will be monitored for this.

433 **9.2 VENIPUNCTURE RISKS**

434 A hollow needle/plastic tube may be placed in the arm for taking blood samples. Blood draws  
435 can cause some common reactions like pain, bruising, or redness at the sampling site. Less  
436 common reactions include bleeding from the sampling site, formation of a small blood clot or  
437 swelling of the vein and surrounding tissues, and fainting.

438 **9.3 FINGERSTICK RISKS**

439 About 1 drop of blood will be removed by fingerstick for measuring blood glucose and  
440 sometimes Hemoglobin A1c (HbA1c) or other tests. This is a standard method used to obtain  
441 blood for routine hospital laboratory tests. Pain is common at the time of lancing. In about 1 in  
442 10 cases, a small amount of bleeding under the skin will produce a bruise. A small scar may  
443 persist for several weeks. The risk of local infection is less than 1 in 1000. This should not be a  
444 significant contributor to risks in this study as fingersticks are part of the usual care for people  
445 with diabetes.

446 **9.4 SUBCUTANEOUS CATHETER RISKS (CGM)**

447 With CGM use participants are at low risk for developing a local skin infection at the site of the  
448 sensor needle placement. If a catheter is left under the skin for more than 24 hours, it is possible  
449 to get an infection where it goes into the skin, with swelling, redness and pain. There may be  
450 bleeding where the catheter is put in and bleeding under the skin causes a bruise (1 in 10 risk).

451 On rare occasions, the CGM may break and leave a small portion of the sensor probe under the  
452 skin that may cause redness, swelling or pain at the insertion site. The participant will be  
453 instructed to notify the study coordinator immediately if this occurs.

454 **9.5 RISK OF HYPOGLYCEMIA**

455 As with any person having diabetes and using insulin, there is always a risk of having a low  
456 blood sugar (hypoglycemia). The frequency of hypoglycemia should be no more and possibly  
457 less than it would be as part of daily living. Symptoms of hypoglycemia can include sweating,  
458 jitteriness, and not feeling well. Just as at home, there is the possibility of fainting or seizures  
459 (convulsions) and that for a few days the participant may not be as aware of symptoms of  
460 hypoglycemia. A CGM functioning poorly and significantly over-reading glucose values could  
461 lead to inappropriate insulin delivery.

462            **9.6 RISK OF HYPERGLYCEMIA**

463            Hyperglycemia and ketonemia could occur if insulin delivery is attenuated or suspended for an  
464            extended period or if the pump or infusion set is not working properly. A CGM functioning  
465            poorly and significantly under-reading glucose values could lead to inappropriate suspension of  
466            insulin delivery. All subjects will be issued a glucose meter and glucose test strips, and a ketone  
467            meter and ketone strips to use to carefully monitor for hyperglycemia and be given instructions  
468            on how to mitigate hyperglycemia should it occur.

469            **9.7 RISK OF DEVICE REUSE**

470            All devices will be used by a single study participant only. There will be no device re-use.

471            **9.8 OTHER RISKS**

472            Some participants may develop skin irritation or allergic reactions to the adhesives used to secure  
473            the CGM, or from tape to secure the insulin infusion sets for the continuous subcutaneous insulin  
474            infusion. If these reactions occur, different adhesives or “under-taping” (such as with IV 3000,  
475            Tegaderm, etc.) will be tried, sites will be rotated frequently, and a mild topical steroid cream or  
476            other medication may be required.

477            Whenever the skin is broken there is the possibility of an infection. The CGM and pump infusion  
478            sites are inserted under the skin. It is possible that any part that is inserted under the skin may  
479            cause an infection. These occur very infrequently, but, if an infection was to occur, oral and/or  
480            topical antibiotics can be used. The risk of skin problems could be greater if you use a sensor for  
481            longer than it is supposed to be used. Therefore, participants will be carefully instructed about  
482            proper use of the sensor.

483            Data downloaded from the CGM, pump, and the home glucose and ketone meter will be  
484            collected for the study as measures of diabetes self-management behaviors. The downloaded data  
485            from the subject's home pump will include data from prior to the date of the screening visit.  
486            Some people may be uncomfortable with the researchers' having such detailed information about  
487            their daily diabetes habits.

488            **9.9 KNOWN POTENTIAL BENEFITS**

489            Participants may experience a significant improvement in glucose control. Hypoglycemia is the  
490            number one fear of many individuals taking insulin and this fear often prevents optimal glycemic  
491            control. Hyperglycemia will likely be reduced as well.

492            It is expected that this protocol will yield increased knowledge about using an automated  
493            closed-loop to control glucose levels in people with type 1 diabetes. The individual participant  
494            may or may not benefit from study participation.

495            **9.10 RISK ASSESSMENT**

496            Based on the facts that (1) adults and adolescents with type 1 diabetes experience mild  
497            hypoglycemia and hyperglycemia frequently as a consequence of the disease and its  
498            management, (2) the study intervention involves periodic automated insulin dosing that may

499 increase the likelihood of hypoglycemia, and periodic automated attenuation of insulin delivery  
500 that may increase the likelihood of hyperglycemia, (3) mitigations are in place, and have been  
501 tested in prior studies using the investigational device system in the home setting, that limit the  
502 likelihood of excessive insulin dosing or prolonged withdrawal of insulin, (4) rapid reversal of  
503 hypoglycemia and hyperglycemia can be achieved, and (5) the Control algorithm (Control-IQ) is  
504 already FDA approved for and has shown significant (10+) TIR improvements in individuals  
505 with type 1 diabetes, it is the assessment of the investigators that this protocol falls under DHHS  
506 46.405 which is a minor increase over minimal risk. In addition, it is the belief of the  
507 investigators that this study also presents prospect of direct benefit to the participants and general  
508 benefit to others with diabetes.

509 **9.11 GENERAL CONSIDERATIONS**

510 The study is being conducted in compliance with the policies described in the study policies  
511 document, with the ethical principles that have their origin in the Declaration of Helsinki, with  
512 the protocol described herein, and with the standards of Good Clinical Practice (GCP).

513

---

Confidential

*Contains trade secrets and/or confidential information exempt from disclosure from 21 CFR 20.61*

514 **10 DESCRIPTION OF THE STUDY DEVICES AND USE**

515 All study supplies will be provided by Tandem Diabetes Care, Inc.

516 **10.1 INSULIN PUMP**

517 The study system will include the Tandem t:slim X2 insulin pump with Control-IQ technology  
518 cleared under K201214 and K200467 respectively (Tandem Diabetes Care, San Diego, CA).

519 **10.2 CONTINUOUS GLUCOSE MONITORING**

520 The study CGM will include Dexcom G6 transmitter and sensors. The CGM sensor will be  
521 replaced at least once every 10 days or as per manufacturer instructions.

522 **10.3 BLOOD GLUCOSE METER AND STRIPS**

523 Blood glucose levels will be measured using the study-assigned blood glucose meter  
524 (glucometer) and the CGM device will be calibrated if needed using the study glucometer  
525 and strips in accordance with the manufacturer's labeling. (Contour NEXT or Contour NEXT  
526 ONE, Ascensia Diabetes Care US, Inc., [name])

527 **10.4 KETONE METER AND STRIPS**

528 Blood ketone levels will be measured using the Abbott Precision Xtra meter and strips in  
529 accordance with the manufacturer's labeling. The blood glucose meter component of the  
530 Precision Xtra device will not be used. (Abbott Diabetes Care Inc., [name],  
531 [name])

532 **10.5 STUDY DEVICE ACCOUNTABILITY PROCEDURES**

533 Device accountability and inventory will be documented in each subject's study chart, to include  
534 detailed inventory records of the study glucose meter, study ketone meter, study CGM supplies,  
535 and Tandem insulin pump system.

536 **10.6 BLOOD GLUCOSE METER TESTING**

- 537 • QC testing will be performed before issuing the blood glucose meter to a subject. Additional  
538 QC testing may be performed per manufacturer guidelines.
- 539 • A tested meter will not be used in a study if it does not read within the target range  
540 concentration per manufacturer labeling.
- 541 • Participants will be reminded to use the study blood glucose meter for all fingerstick blood  
542 glucose measurements.
- 543 • Participants will be asked to perform fingerstick blood glucose measurements in accordance  
544 with the labelling of the study CGM device.

545                   **10.7 BLOOD KETONE TESTING**

546           • QC testing will be performed before issuing the blood ketone meter to a subject. Additional  
547            QC testing may be performed per manufacturer guidelines.

548           • A tested meter will not be used in a study if it does not read within the target range  
549            concentration per manufacturer labeling.

550           • Participants will be instructed on how to perform blood ketone testing.

551           • Participants will be given guidelines for treatment of elevated blood ketones.

552                   **10.8 CGM CALIBRATION**

553           Throughout the study, participants will be instructed to calibrate the study CGM in accordance  
554           with manufacturer labelling.

555                   **10.9 HYPERGLYCEMIA SAFETY PROTOCOL**

556           The t:slim X2 with Control-IQ system will issue a predictive hyperglycemia alert (Control-IQ  
557           High Alert) when the system has increased insulin delivery, but detects a CGM value above 200  
558           mg/dL and does not predict the value will decrease in the next 30 minutes. During the course of  
559           the study, participants will be permitted to change the CGM high glucose threshold alert setting  
560           on their device or mobile app, but will be instructed to choose a value no greater than 300  
561           mg/dL.

562           If the participant receives a Control-IQ High Alert, a prompt appears on the user interface to  
563           check the site for occlusion and test blood glucose.

564           If a participant's CGM reading is  $>300$  mg/dL for more than 60 minutes or is  $\geq 400$  mg/dL at any  
565           point, the participant will be instructed to take the following steps:

566           • Perform a blood glucose meter check.

567           • If the blood glucose is  $>300$  mg/dL, check for blood ketones with the study ketone meter.

568           • If the ketone level is  $\geq 0.6$  mmol/L (or  $\geq 2.5$  mmol/L at any time), take correction insulin,  
569            change insulin (pump) infusion site and contact study staff. Continue to monitor their glucose  
570           and blood ketone levels until they return to normoglycemia and ketones are  $< 0.6$  mmol/L.

571                • If ketones are  $<0.6$  mmol/L, they will be advised to continue to monitor their glucose until it  
572                returns to normoglycemia and to repeat the ketone measurement in 90 minutes if necessary

573           • If correction insulin is administered via insulin syringe, turn Control-IQ off for four hours  
574            and until glucose level has returned to  $<180$  mg/dL.

575                   **10.10 HYPOGLYCEMIA SAFETY PROTOCOL**

576           When using the study device, hypoglycemia low threshold alerts will be set to no lower than 70  
577           mg/dL, and if a participant's CGM reading is  $<70$  mg/dL, subjects will be instructed to treat with  
578           ~15 grams of carbohydrate, and perform fingerstick testing as necessary per CGM manufacturer  
579           instructions.

580 **11 ADVERSE EVENTS, DEVICE ISSUES, AND STOPPING  
581 RULES**

582 **11.1 ADVERSE EVENTS**

583 Adverse Event (AE): Any untoward medical occurrence in a study participant, irrespective of the  
584 relationship between the adverse event and the device(s) under investigation (see section 11.2 for  
585 reportable adverse events for this protocol).

586 Serious Adverse Event (SAE): Any untoward medical occurrence that:

587 Results in death.

588 Is life-threatening; (a non-life-threatening event which, had it been more severe, might have  
589 become life-threatening, is not necessarily considered a serious adverse event).

590 Requires inpatient hospitalization or prolongation of existing hospitalization.

591 Results in persistent or significant disability/incapacity or substantial disruption of the ability to  
592 conduct normal life functions (sight threatening).

593 Is a congenital anomaly or birth defect.

594 Is considered a significant medical event by the investigator based on medical judgment (e.g.,  
595 may jeopardize the participant or may require medical/surgical intervention to prevent one of the  
596 outcomes listed above).

597 Unanticipated Adverse Device Effect (UADE): Any serious adverse effect on health or safety or  
598 any life-threatening problem or death caused by, or associated with, a device, if that effect,  
599 problem, or death was not previously identified in nature, severity, or degree of incidence in the  
600 investigational plan or application (including a supplementary plan or application), or any other  
601 unanticipated serious problem associated with a device that relates to the rights, safety, or  
602 welfare of participants (21 CFR 812.3(s)).

603 Adverse Device Effect (ADE): Any untoward medical occurrence in a study participant which  
604 the device may have caused or to which the device may have contributed (Note that an Adverse  
605 Event Form is to be completed in addition to a Device Deficiency or Issue Form).

606 Device Complaints and Malfunctions: A device complication or complaint is something that  
607 happens to a device or related to device performance, whereas an adverse event happens to a  
608 participant. A device complaint may occur independently from an AE, or along with an AE.  
609 An AE may occur without a device complaint or there may be an AE related to a device  
610 complaint. A device malfunction is any failure of a device to meet its performance specifications  
611 or otherwise perform as intended. Performance specifications include all claims made in the  
612 labeling for the device. The intended performance of a device refers to the intended use for  
613 which the device is labeled or marketed. (21 CFR 803.3). Note: for reporting purposes, sites  
614 will not be asked to distinguish between device complaints and malfunctions.

615            **11.2 REPORTABLE ADVERSE EVENTS**

616    For this protocol, a reportable adverse event includes any untoward medical occurrence that  
617    meets one of the following criteria:

618        1. A serious adverse event  
619        2. An Adverse Device Effect as defined in section 11.1, unless excluded from reporting in  
620        section 11.9  
621        3. An Adverse Event occurring in association with a study procedure  
622        4. Hypoglycemia meeting the definition of severe hypoglycemia as defined below  
623        5. Diabetic ketoacidosis (DKA) as defined below or in the absence of DKA, a  
624        hyperglycemic or ketosis event meeting the criteria defined below

625    Hypoglycemia and hyperglycemia not meeting the criteria below will not be recorded as adverse  
626    events unless associated with an Adverse Device Effect. Skin reactions from sensor placement  
627    are only reportable if severe and/or required treatment.

628    Pregnancy occurring during the study will be recorded.

629            **11.3 HYPOGLYCEMIC EVENTS**

630    Hypoglycemia not associated with an Adverse Device Effect is only reportable as an adverse  
631    event when the following definition for severe hypoglycemia is met: the event required  
632    assistance of another person due to altered consciousness, and required another person to actively  
633    administer carbohydrate, glucagon, or other resuscitative actions. This means that the participant  
634    was impaired cognitively to the point that he/she was unable to treat himself/herself, was unable  
635    to verbalize his/ her needs, was incoherent, disoriented, and/or combative, or experienced seizure  
636    or coma. These episodes may be associated with sufficient neuroglycopenia to induce seizure or  
637    coma. If plasma glucose measurements are not available during such an event, neurological  
638    recovery attributable to the restoration of plasma glucose to normal is considered sufficient  
639    evidence that the event was induced by a low plasma glucose concentration.

640            **11.4 HYPERGLYCEMIC EVENTS/DIABETIC KETOACIDOSIS**

